Potential risk of a seizure: In designing this experiment, we have followed the latest safety guidelines for TMS. Despite these precautions, there is a chance of a seizure as a result of rTMS. Eight seizures have been noted in previous studies, with six of them occurring in healthy volunteers without any history of seizures, brain tumors or traumatic brain injuries. All of these seizures have occurred during rTMS with the participant in the treatment chair and a trained operator on hand. All seizures have stopped by themselves without any medication. No participants have had any problems after the seizures. WFUHS has a plan for dealing with fainting and seizures, and **every TMS researcher involved in providing TMS treatment for this protocol (Key Personnel) will have extensive TMS training from the PI on the study as well as a skills test associated with collecting an accurate motor threshold (which is one of the largest factors that promotes safety).** Additionally, if a participant has a seizure an emergency response team will be called. Most seizures, including those caused by rTMS, last less than 60 seconds and do not require any medication. Participants will be evaluated by a physician associated with the Wake Forest Brain Stimulation Laboratory following recovery from the seizure. Any participant who has a seizure cannot continue with the study.

Other potential risks:

1. **Potential for scalp discomfort and headaches:** Some people report mild discomfort when the magnetic pulses are applied over the scalp. A small number of people (~5%) report headache following rTMS. However, the headaches are temporary and manageable with common over-the-counter pain remedies.
2. **Potential hearing loss: The TMS coil generates a high-energy click that may cause hearing damage.** Humans exposed to TMS have shown temporary increases in auditory threshold (especially at high frequencies) lasting at least 5 minutes and less than 4 hours.
3. **Safety in case of pregnancy:** This protocol will exclude pregnant women. The risks of using TMS with pregnant women are currently unknown. Please inform the research team if you are pregnant or think that you might have become pregnant during the study. A pregnancy test will be performed before the experiment begins.

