4. **Potential for reflex syncopal event:** Syncope is defined as a momentary loss of awareness and postural tone. It typically has a rapid onset, short duration, and spontaneous recovery. Although syncopal episodes are very rare with TMS (less than 1%), they typically occur during the motor

- threshold procedure before the rTMS treatment has begun. Individuals that are sleep deprived and have low or unstable blood pressure are at greater risk.
5. Interaction with electrical or metal implants: Electrically, magnetically or mechanically activated implants (such as cardiac pacemakers), as well as clips on blood vessels in the brain may be affected by rTMS (as well as MRI) and cause pain or abnormal signal propagation. Although the pain has not reported to be significant protocol-approved research study members will conduct a thorough TMS safety questionnaire. This questionnaire will be checked and updated throughout the course of the study. Individuals that have these implants and devices or suspect that they may have pieces of metal in their eyes, head, or body (e.g. bullets, shrapnel, and fragments from metallurgy) will be excluded from the study in order to minimize any discomfort and abnormal signal propagation.

Risks regarding Randomization and Alcohol Related Cues:

Given that participants will be exposed to alcoholic beverages, there may be an added risk of induced cravings. However, it should be noted that the alcohol cues that participants will be exposed to are not as powerful as the daily cues that participant's encounter in their normal living environment. In addition, participants that will be randomized receive the placebo treatment may prove to be less effective than real study treatment(s) or other available treatments.

Risks regarding Confidentiality:

Despite efforts to maintain subjects' anonymity and confidentiality, there is always some minimal risk of people other than the study investigators gaining access to your health information. Every effort will be made to ensure that your health information will be collected and stored in a manner that ensures the highest level of protection of confidentiality.

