Data Entry Methods: Data will be collected using REDCap™, which is a secure web application for building and managing online surveys and databases. REDcap™ supports online or offline data capture for research studies and operations. Participants and protocol-approved study personnel will enter data directly into the online portal to ensure security and prevent data loss.

Data Analysis Plan: Data for this study (behavioral assessments) will be acquired by protocol-approved members of the research team, including graduate students and research specialists. These individuals will also perform data management and analysis under the guidance of the PI. Manuscript composition will be led by the PI and Co-Is, with the assistance of the research team.

Quality Assurance Plan: Weekly meetings will be held between the PIs and research team to discuss any data-related problems as well as qualitative comments received during data collection. Initial data analyses will examine distributions of variable scores, and comparability of baseline characteristics across conditions, any necessary adjustments to analyses will be made. Confidentiality protections are outlined below.

Statistical review of the study will be conducted annually by a Wake Forest biostatistician (including enrollment, retention, assessment inventories).

Definition and Reporting of AEs/SAEs to the IRB/NIH: An adverse event (AE) is defined as any untoward medical occurrence in a study subject who was administered rTMS but does not necessarily have a causal relationship with this treatment. Any unwanted change, physically, psychologically or behaviorally, that occurs in a study participant during the course of the trial is an adverse event. A Serious Adverse Event (SAE) is defined as an adverse event that has one of the following outcomes: death, life-threatening, inpatient hospitalization or prolongation of existing hospitalization, persistent or significant disability/incapacity, a congenital anomaly/birth defect.

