All unexpected AEs will be reported to the Wake Forest Institutional Review Board (IRB) and Committee on Human Research within 48-business hours. Serious AEs will also be reported within 24-business hours. Follow-up of all unexpected and serious AEs will also be reported to these agencies. AEs/SAEs are documented and reported as per IRB requirements. Research staff will identify AEs and obtain all available information to assess severity, seriousness, study relatedness, expectedness, outcome, and the need for change or discontinuation in the study intervention. AEs are documented on AE Logs and AE Case Report Forms. Additional relevant AE information, if available, will be documented in a progress note and stored in the research record as appropriate to allow monitoring and further evaluation. If the AE meets the definition for serious, appropriate SAE protocol specific reporting forms are completed and disseminated to the appropriate persons and within the designated timeframes as indicated above. For each AE/SAE recorded, the research staff will follow the AE/SAE until resolution, stabilization, or until the participant is no longer in the study as stated in the protocol. We will report adverse events to the Medical Wake Forest IRB online per the IRB's guidelines.

Collection and Reporting of AEs and SAEs: As mentioned above, all AEs/SAEs are documented and reported as per IRB requirements. Research staff will identify AEs, verify event with the participant, and

obtain all available information to assess severity, seriousness, study relatedness, expectedness, outcome, and the need for change or discontinuation in the study intervention. AEs are documented on AE Logs and AE Case Report Forms. Additional relevant AE information, if available, will be documented in a progress note and stored in the research record as appropriate to allow monitoring and further evaluation. If the AE meets the definition for serious, appropriate SAE protocol specific reporting forms are completed and disseminated to the appropriate persons and within the designated timeframes as indicated above. If applicable, copies of medical records and injury reports will be retrieved and safely stored in the subjects file. De-identified copies of reports will be sent to the Wake Forest IRB and ME/DSBM. For each AE/SAE recorded, the research staff will follow the AE/SAE until resolution, stabilization, or until the participant is no longer in the study as stated in the protocol.

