Reporting of Unanticipated Problems, Adverse Events or Deviations: Any unanticipated problems, serious, and/or unexpected AEs, deviations or protocol changes will be reported within 24-72 business hours, depending on severity, by the principal investigator or designated member of the research team to the Wake Forest IRB, ME/DSMB and to the sponsor, NIH.

Management of SAEs or Other Study Risks: As described above, SAEs will be immediately reported, within 24 business hours, to the ME/DSBM, sponsor and Wake Forest IRB. For each SAE recorded, the research staff will follow the SAE until resolution, stabilization, or until the participant is no longer in the study as stated in the protocol. If applicable, copies of medical records and injury reports will be retrieved and safely stored in the subjects file. De-identified copies of reports will be sent to the Wake Forest IRB, ME/DSBM, and NIH.

Reporting of IRB Actions and ME/DSMB Reports to NIH: Any IRB actions and ME/DSMB reports will be reported to both the Wake Forest IRB and the NIH Institute supporting the study following the sponsor's report submission guidelines, should this study be awarded.

Report of Changes or Amendments to the Protocol: Any changes to the proposal/protocol must be approved by the NIH Institute supporting the study. Any amendments to the IRB protocol associated with the proposed work will be reported to NIH should this proposal be awarded funding.

Trial Stopping Rules: The protocol will immediately be paused following notification of a SAE. Per IRB policy, the IRB and ME/DSMB will be notified within 24 business hours following the SAE notification. SAEs will be reported to NIH within 72 hours. Should the reported SAE be confirmed as directly related to the protocol, the trial will be terminated. The device manufacturer will be notified within 72 business hours. Of note, according to the literature associated with the MagVenture device, there have been no clinical trials stopped or SAEs reported.

Conflict of Interest: Neither the PI, nor members of the research team have any Conflicts of Interest directly related to this protocol. The rTMS device used for the proposed study is manufactured by MagVenture.

Reporting of Unanticipated Problems, Adverse Events or Deviations

Any unanticipated problems, serious and unexpected adverse events, deviations or protocol changes will be promptly reported by the principal investigator or designated member of the research team to the IRB.

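### An iTBS-caused seizure that is not classed as serious requires no pause of the trial, while the same seizure followed by admission ends it

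*Combined protocol and SAP*

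**What the plan says.** Under Data and Safety Monitoring, the paragraph on Trial Stopping Rules has two steps. The pause: "The protocol will immediately be paused following notification of a SAE". The stop: "Should the reported SAE be confirmed as directly related to the protocol, the trial will be terminated". No other event is named as a reason to pause or stop the trial.

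The trigger is defined under Definition and Reporting of AEs/SAEs to the IRB/NIH: "A Serious Adverse Event (SAE) is defined as an adverse event that has one of the following outcomes". The outcomes that follow are death, threat to life, inpatient admission or a longer stay, lasting disability, and birth defect.

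The paragraph on the potential risk of a seizure (Risks to subjects) counts eight earlier rTMS seizures and reports no later problems in those participants. It adds: "All seizures have stopped by themselves without any medication" and "Most seizures, including those caused by rTMS, last less than 60 seconds and do not require any medication". If one occurs here, an emergency response team is called and a physician evaluates the participant after recovery. The consequence for study conduct is: "Any participant who has a seizure cannot continue with the study".

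Three other provisions matter:
- For every adverse event, staff assess seriousness, relatedness and expectedness, and whether the intervention needs to be altered or stopped.
- Adverse events go to the IRB under that board's guidelines, with a fixed deadline for some: "All unexpected AEs will be reported to the Wake Forest Institutional Review Board (IRB) and Committee on Human Research within 48-business hours".
- The investigator asks about safety and tolerance at weekly team meetings.

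**The concern.** Seizure is the device risk for which the protocol writes its own emergency plan. Yet whether the trial must pause after one depends on how the event is classed, and in practice largely on whether the participant is admitted. That decision may rest with emergency clinicians outside the study. It says little about whether stimulation at these settings is safe for the next person.

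At stake is the safety of later participants. After a stimulation-induced seizure that is handled as non-serious, the next participant could be stimulated without any required halt. In the other direction, a short precautionary admission would end the trial automatically once relatedness was confirmed.

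**Working it through.** This is mainly a check of text against text.

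**Step 1. Apply the SAE definition to the seizure the protocol describes.** A seizure that lasts under a minute, stops unaided and leaves no after-effects is not a death, a lasting disability or a birth defect. Two outcomes remain open: threat to life, which is a judgement, and admission, which is a disposition. No item covers a medically important event that has neither outcome.

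**Step 2. Apply the stopping rule.**

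| Event | SAE? | Required pause? | Required termination? |
|---|---|---|---|
| iTBS-caused seizure, resolves, sent home, not judged life-threatening | No | No | No |
| Same seizure, sent home, judged life-threatening | Yes | Yes | Yes, once relatedness is confirmed |
| Same seizure, admitted | Yes | Yes | Yes, once relatedness is confirmed |
| Unrelated admission during the trial | Yes | Yes | No |

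The first and third rows share the same cause and the same clinical course but have opposite consequences for the trial. The last row shows that an event unrelated to stimulation does pause it. The rule does not say who confirms relatedness.

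**Step 3. Look for another route to a mandatory pause.**
- The seizure paragraph removes the affected participant and is silent on the trial.
- Emergency response and physician evaluation protect that participant, not the next one.
- The 48-business-hour report covers unexpected events. A seizure is a listed risk, so that deadline does not clearly apply, although the general commitment to report adverse events to the IRB does.
- The assessment of whether to alter or stop the intervention applies to every adverse event, but it has no criteria and imposes no halt.
- The weekly meeting is a review, not a hold.

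**Step 4. Size.** Inputs from Sample Size: 48 participants, 24 of them on real iTBS, 3 to 4 recruited per month.
- Real sessions per month: 3/2 = 1.5 to 4/2 = 2. With a 30-day month, that is one every 30/2 = 15 to 30/1.5 = 20 days on average.
- Real sessions still to come after a seizure: 0 to 23. If each session is equally likely to be the one, the mean is (0 + 1 + … + 23)/24 = 11.5.
- Chance of at least one seizure in 24 real sessions: 1 − (1 − p)^24. The eight earlier seizures have no denominator, so p is purely an assumption. p = 0.01% gives 0.2%; p = 0.1% gives 2.4%; p = 1% gives 21%. Nothing in the documents supports the top of this range. Motor-threshold testing, which both groups undergo, is not counted.

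**The case against.** The strongest reply is that the plan does not leave a non-serious seizure unattended. Staff must assess each adverse event for seriousness and for whether the intervention should change or stop. Adverse events are reported to the IRB, and de-identified reports go to the IRB and ME/DSMB. With real sessions 15 to 20 days apart on average, a weekly safety meeting would normally fall before the next one. Any rule based on SAEs treats admitted and non-admitted events differently, and discretion is the usual route for the rest.

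Much of this stands. A reader might infer that the next participant would be stimulated with no review at all, or that the seizure would go unreported. The documents do not support either reading. A reader might also infer that every seizure with discharge home escapes the pause. That goes too far as well: threat to life is listed separately from admission, so a seizure in someone sent home could still be classed as serious, although the protocol's own description makes that less likely.

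What the reply does not supply is a mandatory halt. The assessment has no criteria, a report is not a pause, and average spacing does not prevent two sessions in the same week. The sponsor chose to write explicit stopping rules, and they do not cover this case.

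**Conclusion.** The point holds as a limited gap in the safety rules. A self-limiting iTBS-caused seizure that is not judged life-threatening carries no mandatory pause when the participant goes home. The same seizure pauses and then terminates the trial when the participant is admitted and relatedness is confirmed. Existing review is discretionary.

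The conclusion rests on three assumptions: the stopping rule is followed as written, the seizure runs the course that the protocol describes, and no IRB policy outside the documents imposes its own pause. The seizure probabilities above only illustrate the scale, because the documents contain no rate. The number of later real sessions, at most 23, is likewise an exposure only if nobody acts on the discretionary review. A reader might look for an effect on power or on the analysis; none follows from this. It is a worthwhile, inexpensive improvement and not a flaw that undermines the trial.

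**What to change.** Make two linked changes, in the SAE definition and in the Trial Stopping Rules:

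1. Any seizure from the start of motor-threshold testing to the end of Visit 2 is handled as an SAE for the pause and for the 24-business-hour report to the IRB and ME/DSMB, whatever its outcome or the participant's disposition.
2. For a related seizure there is one consequence, regardless of admission: stimulation stays paused until the IRB and ME/DSMB agree that it may resume. The same sentence should say who confirms relatedness.

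The second change fits the seizure paragraph, which withdraws the participant and so implies that the study may go on. It also replaces automatic termination after an admitted, related seizure with a decision by the two boards, and the sponsor should adopt that knowingly.

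The cost is protocol wording and an IRB amendment. The main downside is a false alarm: a syncope during motor-threshold testing could be taken for a seizure. The protocol puts syncope below 1%. At that ceiling, the chance of at least one among 48 participants is 1 − 0.99^48 = 38%, and only those mistaken for a seizure would pause anything. The pause should end as soon as the physician evaluation already planned after a seizure, extended to suspected seizures, finds that there was none.
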